8 OUTLINE OF STUDY PROCEDURES

Patients will be recruited from specialized study sites, equipped with an intensive care unit and access to a bone marrow transplant unit.

Patients will be in the treating unit the day before the first administration of emapalumab (Study Day minus one, SD-1).

For a detailed description of the schedule of visits and assessments, refer to the Schedule of Assessment Table 1 (Screening and Treatment Period) and Table 2 (Follow-up Period).

Informed consent form must be signed by the patient or his/her legally authorized representative prior to any study-related procedures, with the assent of patients who are deemed suitable to provide it.

During the emapalumab treatment period, visits for infusion and efficacy/safety assessments will occur on SD0, SD3 and twice-a-week thereafter (not more than 4 days apart). In the circumstances when HSCT is scheduled beyond 12 weeks from emapalumab initiation and Complete Response is maintained (see Section 5.3), the treatment with emapalumab may continue once a week; acceptable time-window for visits in this case will be ± 1 day. An EOT visit has to be performed 3 ± 1 days after last emapalumab infusion.

Furthermore, during the follow-up period, the following time-windows are allowed around visits:

- Pre-conditioning: can be combined with EOT visit provided the two visits are

not more than 2 days apart

Week (Wk) 1-2-3, D+30 post-HSCT: ±2 days
 D+60, D+100 post-HSCT: ±1 week
 6-mo, 1-yr post-HSCT: ±4 weeks

If HSCT is not performed, the described schedule applies to the follow-up visits required to occur after the last emapalumab infusion.

Following windows can be applied to the vital signs measurement:

When measured every 15 minutes: ±5 minutes
 When measured every 30 minutes: ±10 minutes

- When measured at 1 hour and 2 hours after infusion: \pm 15 minutes

Some procedures are not to be done systematically but only if clinically relevant. For example:

- ECG is mandatory at Screening and at EOT visits, however it should be done at any other timepoint during the study, if deemed appropriate.
- Brain magnetic resonance imaging (MRI) is mandatory at Screening only in case of CNS disease, but should be done at any other time-points during the study to monitor evolution or to confirm onset of CNS involvement, as clinically indicated.

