The following assessments are to be performed post-infusion at Visit 3 and onwards:

Vital sign assessment:

 Heart rate, oxygen saturation, blood pressure and temperature at the end of the infusion, 1 hour and 2 hours after completion of emapalumab infusion

PK:

 Emapalumab serum concentration (every other infusion starting from Visit 3)

Clinical Assessment:

 QOL questionnaire - PedsQL[™], Pediatric Quality of Life Inventory[™] (at Visit 3 only)

During treatment, emapalumab and biomarker concentrations may be measured in other matrices, such as CSF or BAL, if samples obtained in procedures which are performed for diagnostic/therapeutic purposes can also be available for these exploratory investigations, and if clinically indicated.

8.5 WEEK 8 ASSESSMENT VISIT (3 DAYS AFTER WEEK 8 INFUSION) AND END OF TREATMENT VISIT (3 DAYS AFTER LAST EMAPALUMAB INFUSION)

These visits will include a full patient's assessment.

The Week 8 Assessment Visit will be performed 3 (± 1) days after the last Week 8 emapalumab infusion. If treatment with emapalumab is completed before Week 8, only an EOT visit will be performed 3 (± 1) days after the last infusion.

For patients continuing treatment beyond Week 8, an EOT visit will be conducted 3 (± 1) days after the last emapalumab infusion.

The following assessments are to be performed at the Week 8 Assessment Visit and at the EOT Visit:

Clinical Assessment:

- Vital signs, including body temperature, heart rate, blood pressure, and oxygen saturation
- Physical examination, including as a minimum, weight, spleen and liver size (by abdominal palpation), and neurological examination
- Assessment of clinical response
- QOL questionnaires PedsQL[™], Pediatric Quality of Life Inventory[™],
 BASES (BASES only at EoT and if HSCT is planned)

Procedure:

ECG (only at EOT)

Search for infections:

- TB by PCR (if not performed within the last 4 weeks)
- Infection search & monitoring in case of suspicion of infection or if there is an active infection at screening/baseline to monitor evolution of viral load and positivity for an identified pathogenAtypical mycobacteria, Histoplasma Capsulatum, Shigella, Salmonella, Campylobacter, Leishmania – only if an infection is suspected

Study NI-0501-09 NI-0501 in Primary HLH Page 54 of 92

Laboratory:

 CBC with differential count (including large unstained cells count, whenever performed as routine)

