11.3.1 Efficacy Data

The analysis of the primary endpoint, Overall Response Rate, will utilize an exact binomial test to evaluate the null hypothesis that the response rate is at most 40%. This test will be undertaken at the one-sided 0.025 level.

Time to Response, Duration of Response, and Survival time will be presented using Kaplan-Meier curves with medians calculated if available. Ninety-five percent confidence intervals will be calculated for the median for each of these endpoints.

For maintenance of response achieved any time during the study, event of interest will be the loss of response, with patients in response being censored on the day starting conditioning.

Additional endpoints based on binary outcomes including number of patients who reduce glucocorticoids by 50% or more, and number of patients able to proceed to HSCT will be converted to proportions and associated 95% confidence intervals calculated.

Statistical significance in terms of p-values will only be obtained for the primary endpoint in both the All Treated and the Evaluable analysis sets. All other endpoints will be viewed as supportive for the primary endpoint and as a consequence no formal hierarchy of endpoints will be declared.

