6.1.4. Handling of Dropouts or Missing Data

[figure not shown]
While all possible efforts will be made to ensure that patients stay in the study and all data is collected as scheduled, the occurrence of missing data cannot be completely eliminated.

Rules for handling missing or partial AEs or birth dates are described in Section 6.1.10

For defining the primary efficacy endpoint (Overall Response, see Section 6.1.9.4 for definition), values of some parameters may be missing, thus impacting the response assessment. Imputation rules for assessing disease response at EOT or Week 8 (whichever occurs earlier) and throughout the study have been pre-defined as follows. Note: Imputed values will be flagged in the listings for all endpoints where applicable.

Response at EOT or Week 8 (whichever occurs earlier):

- Missing data at EOT/Week 8 for the parameters relevant to assessment of Overall Response will be imputed by the closest available value from the EOT/Week 8 target day (as per Table 1 and Table 2) up to 8 days, provided upper window limit is before start of conditioning. For body temperature, in the event of repeated measures recorded on the same study day, the highest value will be selected.
- No imputation will be applied if no value is available within the time of the EOT/Week 8 target day up to 8 days. That parameter will be viewed as missing and complete response will not be assigned, even if all other parameters are normal.
- Values recorded at both scheduled and unscheduled visits will be considered.

• If all parameters are unable to be imputed then the overall response assessment will be recorded as missing.

Response throughout the study:

- For secondary time to event analyses (e.g., duration of response, time to response), both scheduled and unscheduled visits will be used for assessment of response.
- If a numerical parameter (i.e. Body Temperature, D-Dimer, Fibrinogen, Ferritin, Platelets, Neutrophils) needed for the response assessment is missing, the midpoint approach will be used to estimate the missing value i.e., the last observed value before the missing period will be averaged with the first value available after the missing period. This rule will be applied to parameter values missing for a period of up to a maximum of 7 consecutive days.

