* end of study, or any time during follow-up period (including withdrawal of consent)				

Table 11: Event-Free Survival

• Duration of Response (i.e. maintenance of response achieved at any time during the study until EOT) is defined as the total elapsed time from achievement of first Overall Response to first loss of response, pending the duration of this response is at least 4 days. If the first observed response does not last for at least 4 days, then the next response period will be considered. Similarly, loss of response should persist for at least 4 days, otherwise the next loss of response period will be considered. Patients who are in response at EOT will be censored at that date. Patients who do not achieve at least HLH improvement once between the date of first dose and EOT will be excluded from the analysis.

The analysis start and end dates and the censoring rules for calculation of duration of response are described in the following scheme:

Situation	Outcome (event or censored)	Analysis start date	Analysis end date
Maintained loss of overall response	Event	Date of first response ²	Date of loss of overall response ²
Death for any cause	Event	Date of first response ²	Date of death
In response at the end of the observation period ¹	Censored	Date of first response ²	Last known response

Table 12: Duration of Response

AD-ST-33.06 Effective date: 12-Nov-2020

¹ end of treatment without conditioning, or start of conditioning for HSCT, or early termination (including withdrawal of consent);

[figure not shown]
² last for at least 4 days

- Cumulative Duration of Response = Total time in response from the first achievement of an Overall Response until HSCT conditioning (or EOT if the patient did not have HSCT performed). Considering patients who achieve a response, lost that response, and then achieve it subsequently, the total time in response will be calculated by adding together these separate periods in response. Patients who do not achieve response at least once between the date of first dose and the time of conditioning start are excluded from the analysis.
- Percent days in response = Cumulative response duration divided by number of days from first infusion until HSCT conditioning (or EOT if the patient did not have HSCT performed).

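### Duration of Response: a loss first seen at end of treatment, and often one first seen at the last infusion, cannot meet the 4-day rule by EOT, and SAP Table 12 gives it no outcome

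*SAP*

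**What the plan says.** **The loss rule.** SAP 6.1.9.4 defines Duration of Response as the time from first response to first loss, up to EOT. On the loss it says "loss of response should persist for at least 4 days, otherwise the next loss of response period will be considered". Footnote 2 of Table 12 attaches the same 4-day condition to the date of loss.

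**The outcomes.** Table 12 has three rows: a maintained loss (event), death (event), and still in response when observation ends (censored at the last known response). Footnote 1 ends observation at "end of treatment without conditioning, or start of conditioning for HSCT, or early termination (including withdrawal of consent". The running text puts it differently: "Patients who are in response at EOT will be censored at that date".

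**The protocol's version.** Protocol 11.3.1 takes loss of response as the event, sets no minimum duration for it, and proceeds "with patients in response being censored on the day starting conditioning". SAP section 11, which lists changes from the planned analysis, does not mention the persistence condition.

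**The visit schedule.** Protocol section 8: "visits for infusion and efficacy/safety assessments will occur on SD0, SD3 and twice-a-week thereafter (not more than 4 days apart"; then "An EOT visit has to be performed 3 ± 1 days after last emapalumab infusion". Protocol 8.5 repeats that interval for treatment that runs past Week 8. For time-to-event endpoints SAP 6.1.4 states that "both scheduled and unscheduled visits will be used for assessment of response". If no EOT visit took place, SAP 6.1.5 uses the day of the last infusion as EOT.

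**Unconfirmed states.** SAP 6.1.4 treats a response that cannot be confirmed for 4 days because of missing data as lost. It has no matching rule for a loss that cannot be confirmed.

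**The concern.** The persistence rule needs 4 days of observation after the loss, but the window that closes the endpoint is only 2 to 4 days wide. When the loss comes at the very end of treatment, there is also no next loss period for the rule to move on to. The patient has visibly failed, yet does not satisfy the event definition.

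A Kaplan-Meier analysis needs every responder to be an event or censored. If the table offers no event, the programmer's natural default is the only censoring row, dated at the last known response. Censoring would then be tied directly to failure, which is informative, and the curve and median would be too high. With about 22 responders expected (65% of 34), a few patients handled this way would be visible.

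**Working it through.** The plan states no figure for this point, so there is none to reproduce. The check has four steps.

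**1. Days of loss observable by EOT**

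Inputs: gap between infusions g = 3 or 4 days (Protocol section 8: twice weekly, at most 4 days apart); EOT offset e = 2, 3 or 4 days (same section); required persistence 4 days (SAP 6.1.9.4). The SAP does not say how the 4 days are counted, so both conventions are shown.

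| Loss first documented at | Days to EOT | Elapsed count (days ≥ 4) | Inclusive count (days + 1 ≥ 4) |
|---|---|---|---|
| Penultimate infusion | g + e: from 3 + 2 = 5 to 4 + 4 = 8 | always met | always met |
| Last infusion | e: 2, 3 or 4 | met only if EOT is on day +4 | met if EOT is on day +3 or +4 |
| EOT visit | 0 | not met | not met (0 + 1 = 1) |

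- Once-weekly dosing with its ± 1 day window (gap 6 to 8): a loss at the penultimate infusion has 6 + 2 = 8 to 8 + 4 = 12 days and qualifies.
- No EOT visit (EOT = last infusion day): a loss at the penultimate infusion has g = 3 or 4 days. It qualifies at 4, and at 3 only by inclusive counting. A loss at the last infusion has 0 days.

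**2. Which Table 12 row applies to a loss that falls short**

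- Maintained loss: no, because 4 days have not been shown.
- Death: no.
- In response at the end of observation: no, because the last assessment shows non-response.

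No row applies. The running text also censors only patients who are in response.

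**3. Could later visits confirm the loss?**

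Protocol 8.6.2 gives patients without HSCT visits at weeks 1, 2 and 3 after the last infusion, with a ± 2 day window. Week 1 falls on days 5 to 9 and EOT on days 2 to 4, so the interval is 5 − 4 = 1 to 9 − 2 = 7 days (nominally 7 − 3 = 4). Week 2 falls on days 12 to 16, giving 12 − 4 = 8 to 16 − 2 = 14 days. These visits could settle the question, but the SAP does not say they may be used, and both its text and footnote 1 end the endpoint at EOT for these patients.

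**4. Possible size if such losses are censored (illustration, all inputs assumed)**

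Take 22 responders, exponential time to loss with mean 150 days, follow-up from response to EOT uniform on 21 to 150 days, and a share p of losses that are terminal and censored, independent of when they occur. The 60-day estimate is then exp(−(1 − p) × 60/150).

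The chance of an observed loss is 1 − (150/129) × (e^−0.14 − e^−1.00) = 0.417, or 0.417 × 22 = 9.2 expected losses. Of these, (1 − p) × 9.2 are counted.

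| p | Events counted | 60-day Kaplan-Meier |
|---|---|---|
| 0 | 9.2 | exp(−0.40) = 0.67 |
| 10% | 8.3 | exp(−0.36) = 0.70 |
| 25% | 6.9 | exp(−0.30) = 0.74 |
| 50% | 4.6 | exp(−0.20) = 0.82 |

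A simulation of 20,000 patients gave the same Kaplan-Meier values to two decimals.

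**The case against.** The strongest reply is that the SAP nowhere says persistence must be shown by EOT, and nowhere says these patients are censored. Post-treatment visits exist that could confirm a loss, and the nearest written rule, that an unconfirmed response is assumed lost, leans the conservative way. The protocol also foresees dose increases and added HLH treatment while emapalumab continues. Losses managed that way are seen over several visits and meet the rule. The endpoint is secondary and supportive with no p-value. Cumulative duration and percent days in response carry no loss-persistence condition, and swimmer plots will show each patient's course.

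Much of this stands. A reader might infer that losses which end treatment are never events. The documents do not support that: losses from the penultimate infusion or earlier qualify when an EOT visit is done, some last-infusion losses qualify, death always counts, and Table 12 observes HSCT patients to the start of conditioning. (That relief is partial. The text still stops at EOT, and Protocol 8.6.1 lets the pre-conditioning visit be combined with EOT.) A reader might also infer that the SAP censors these patients and so certainly overstates duration. It does not say so, and nothing in the documents shows how often a response ends this way.

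What the reply does not remove is the gap. The rule for unconfirmed responses concerns missing data; it does not classify an observed loss after an established response. Silence on post-EOT data is not permission to use it.

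**Conclusion.** Wrong as written, within a limited scope. The stated rule withholds event status from an observed failure at EOT, and often from one at the last infusion, and then assigns that patient nothing. Under Protocol 11.3.1 the same patient would be an event. This is more than a missing detail, because a responder who is not an event in a Kaplan-Meier analysis is in practice censored.

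Overstatement follows only if that default is taken, and its size is not established. It depends on the terminal share of losses, which the documents do not give. In the illustration the 60-day estimate rises by 0.03, 0.07 or 0.15 at shares of 10%, 25% or 50%, and not at all at 0%. Duration of Response is descriptive, and the primary test of response is untouched.

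**What to change.** Add to SAP 6.1.9.4, with a matching event row in Table 12:

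> A loss of response still present at the last available assessment in the observation period, with no later assessment showing response regained, is an event dated at the first non-response assessment.

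In the same edit:

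- state whether the 4 days are counted as elapsed or inclusive;
- state whether visits after EOT may confirm a loss;
- reconcile the censoring date, which is EOT in the text, the last known response in Table 12 (with observation to the start of conditioning for HSCT patients), and the start of conditioning in Protocol 11.3.1.

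Nothing wider is needed. Making discontinuation or a new HLH treatment override the persistence rule would redefine the endpoint.

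Cost: one sentence, one table row and three clarifications, with no new data. Duration of Response may become slightly less favourable, and an occasional transient dip at the last visit will count as a loss.

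### SAP 6.1.9.4 gives conflicting end dates for Duration of Response: end of treatment in the prose, start of conditioning in Table 12 and the protocol

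*SAP*

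**What the plan says.** Within SAP 6.1.9.4 the end of Duration of Response is given in three ways:

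- **Prose.** The measure is "maintenance of response achieved at any time during the study until EOT", and "Patients who are in response at EOT will be censored at that date".
- **Table 12, footnote 1.** The observation period closes at "end of treatment without conditioning, or start of conditioning for HSCT, or early termination (including withdrawal of consent" (closing bracket omitted).
- **Table 12, end-date cell of the censored row.** "Last known response".

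The next definition, Cumulative Duration of Response, is "Total time in response from the first achievement of an Overall Response until HSCT conditioning", with EOT used only if no HSCT was performed. The entry rules differ as well. Patients without a response "between the date of first dose and EOT will be excluded from the analysis" for the first measure; for the cumulative measure the window is "between the date of first dose and the time of conditioning start are excluded from the analysis".

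Elsewhere the documents agree with one another. SAP 2.2.1.2, protocol 7.1 and protocol 11.3.1 all censor event-free responders at start of conditioning. SAP section 11 lists seven changes from the protocol. One adds the cumulative measure; none moves the censoring date of Duration of Response to EOT.

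**The concern.** A programmer working from the prose and one working from Table 12 would derive different dates for the same conditioned patient, and in some cases a different event status. Following the prose would depart from the endpoint that the protocol defines, without a declared change. The planned outputs could also disagree: one unbroken response could have one length in table 14.2.4.1 (Duration of Response) and another in table 14.2.4.2 (Cumulative Duration). If this is left open, the choice falls to whoever programs it, in an open-label study whose data are visible.

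**Working it through.** The plan states no figure to reproduce. The check compares the rules and then applies date arithmetic.

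**1. Can EOT and start of conditioning differ?** Yes.
- Protocol section 8 places the EOT visit 3 ± 1 days after the last infusion.
- SAP 6.1.5 takes EOT as that visit or, if none was held, the day of the last infusion.
- Protocol 8.6.1 allows the pre-conditioning visit to be separate from EOT; the two may be merged only if no more than 2 days apart.
- Protocol 3.3 requires no wash-out, so the gap can be very short. It also caps treatment at 6 months, and protocol 10.1.3 lets the investigator stop treatment at any time, so the gap can be long.
- No maximum gap is stated.

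**2. Effect on the censored duration.** Assumed patient: response from day 10, EOT on day 60, still in response at conditioning g days after EOT. Prose: 60 − 10 = 50. Conditioning rule: (60 + g) − 10.

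| Assumed gap g (days) | Prose | Conditioning rule | Difference |
|---|---|---|---|
| 0 | 50 | 50 | 0% |
| 2 | 50 | 52 | 2/50 = 4% |
| 7 | 50 | 57 | 7/50 = 14% |
| 21 | 50 | 71 | 21/50 = 42% |

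Cumulative Duration for the same unbroken response equals the conditioning-rule column. If the patient was in response at the EOT assessment, the last known response lies between 50 days and that figure. Counting both end days would add 1 to every duration and leave the differences in days unchanged.

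**3. Effect on event status.** The prose requires that "loss of response should persist for at least 4 days".
- *Loss after EOT.* Response from day 10, EOT day 60, sustained loss from day 70, conditioning day 81. The prose censors at 50 days. The conditioning rule records an event at 70 − 10 = 60 days.
- *Loss just before EOT.* Loss from day 58, EOT day 60, conditioning day 62. If persistence must be shown inside the observation window, only 2 days have accrued at EOT and 4 at conditioning. An event at 58 − 10 = 48 days is confirmed only under the conditioning rule.
- *Death after EOT.* Table 12 has a row counting death from any cause as an event, with no time limit. The prose censors a responder at EOT whatever follows. Protocol 11.3.1 names only loss of response as the event. A patient who dies between EOT and intended conditioning was never conditioned, so footnote 1 also closes observation at end of treatment while the death row does not. Choosing start of conditioning therefore does not by itself settle this case.

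**4. Can such losses be observed?** Protocol Table 2 schedules one visit between EOT and HSCT, the pre-conditioning visit. One visit cannot show a loss lasting 4 days, and the numerical and character imputation in SAP 6.1.4 stops at 7 consecutive days. A loss arising wholly in the gap would usually need unscheduled assessments, which SAP 6.1.4 does allow for this endpoint.

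**5. Two lesser points.**
- Protocol 7.1 and SAP 2.2.1.2 include survival after the last infusion, for patients without HSCT, within Overall Survival. SAP 8.2.1 plans no analysis from that time origin, and section 11 does not say so.
- SAP 6.1.4 gives a 1-day duration to patients whose response cannot be confirmed for 4 days because of missing data, whereas SAP 8.2.4 limits the analysis to confirmed responses.

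**The case against.** The strongest reply is that the rule is already largely settled. The SAP introduces Table 12 as the statement of the censoring rules, and footnote 1 agrees with the protocol. The last-known-response cell can be read as compatible with it: observation closes at conditioning, and the date used is the last assessment in response. On that view the defect is stray prose about a descriptive endpoint with no p-value.

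Much of this stands, and it limits the weight of the point. But no precedence rule ranks the table above the prose, which is explicit. The last assessment in response is a defensible convention, but it is not the protocol's date. The death row and the differing entry windows remain open on either reading.

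It is also fair to say that the sizes rest on assumed gaps, and that long gaps will contain few assessments. The 21-day row and the day-70 example are illustrations, not expected values.

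Several stronger readings are tempting, but the documents do not support them:
- *Event status can differ only if conditioning starts at least 4 days after EOT.* The death row has no 4-day condition, and a loss that begins before EOT can complete its 4 days in a shorter gap.
- *With no wash-out, conditioning may precede the EOT visit, so the prose gives the longer duration.* SAP 6.1.5 describes the EOT date as one before start of conditioning, so this case should not be relied on.
- *Table 12 footnote 2 excludes patients with unconfirmed responses.* It is attached to the response and loss dates and excludes nobody. Only the restriction in 8.2.4 is in tension with the 1-day rule, which can be read as a specific missing-data exception.
- *Survival of patients without HSCT goes unanalysed.* Their deaths and follow-up are counted from first dose in Tables 8 and 9, and listed. Only the second time origin is absent.

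**Conclusion.** The contradiction is real, lies in current text, and should be corrected. It affects patients who go on to conditioning and, through the death row, responders who die after EOT without reaching it. For conditioned patients still in response, the difference in censored duration equals the gap from EOT to conditioning: none when the dates coincide, and 2, 7 or 21 days in the assumed cases. Some patients may also change between censored and event. How many cannot be derived, because the documents give neither the distribution of the gap nor the rate of loss within it. Duration of Response is secondary and descriptive, and nothing here touches the primary test. The two lesser points have no derivable size or direction.

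**What to change.** In SAP 6.1.9.4, before database lock:

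1. Delete the EOT limit from the definition of Duration of Response, and delete the sentence that censors at EOT.
2. Censor responders at start of conditioning, or at EOT only if there is no conditioning.
3. Align the Table 12 end-date cell, keeping the last known response only for early termination.
4. Use the same entry window as Cumulative Duration of Response, so that a response first seen between EOT and conditioning is treated alike in both.
5. State how a death after EOT is counted, and reconcile the death row with footnote 1 and protocol 11.3.1.
6. State how a loss first seen at the pre-conditioning visit is handled under the 4-day persistence rule.

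Lesser edits:
- Add one line to section 11 saying that survival after the last infusion without HSCT is covered only by the from-first-dose analyses in Tables 8 and 9.
- Amend 8.2.4 so that its restriction to confirmed responses is consistent with the 1-day missing-data rule in 6.1.4.

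The cost is SAP wording only. No new data collection is required: the pre-conditioning visit already collects vital signs, spleen size, blood counts, coagulation and ferritin. For long gaps, however, confirming a 4-day loss will depend on whatever unscheduled assessments exist, and the SAP should say so.
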